#### 7.4.4 Early Patient Termination/Patient Withdrawal

Patients who discontinue study treatment will be asked to have all end-of-treatment assessments performed as described in the protocol (see [Assessment Schedule](#)). If a patient discontinues treatment during Cycle 1 due to any reason other than a DLT and does not meet the minimum requirements for inclusion in the MTD determining population described in Section 5.1.3, that patient will be replaced.

#### 7.5 ECG Measurements

For each set of triplicate ECGs, three standard resting 12-lead ECGs will be obtained not more than 3 minutes apart each from the previous ECG. ECGs will be obtained after the patient has been resting quietly in semi-supine or supine position for at least 5 minutes before the first ECG and during the triplicate. When ECG and PK assessments coincide, ECGs must be done **within** 10 minutes **before** the scheduled PK sample. When ECG and blood draws other than PK coincide, ECGs should be done before these blood draws, however these blood draws (other than PK) may be taken more than 10 minutes after ECGs, or ECGs may be done more than 10 minutes after these blood draws (other than PK). ECG parameters to be recorded are: Heart rate; RR, PR, and QT intervals; QRS duration; ECG body position; interpretation of ECG. Depending on the emerging ECG data during dose escalation, ECGs may be transmitted to a central reading vendor, as an option.

Triplicate ECG measurements will be collected at the following time points:

*CONFIDENTIAL*

- Screening
- Cycle 1 Day 1: Pre-dose and after end of infusion (EOI), and 2, 4, and 7 hours ( $\pm 15$  minutes) after EOI
- Cycle 1 Day 2: 24 hours ( $\pm 2$  hours) after the start of Day 1 infusion
- Cycle 1 Days 4, 8, and 15 ( $\pm 1$  day)
- Cycle 1 Day 22: only in patients with planned PK assessment
- Cycle 2 Day 1: Pre-dose and after EOI
- Cycle 2 Days 8 and 15 ( $\pm 2$  days)
- Cycle 2 Day 22: only in patients with planned PK assessment
- Cycle 3 Day 1: Pre-dose and after EOI, and 2, 4, and 7 hours ( $\pm 15$  minutes) after EOI
- Cycle 3 Day 2: 24 hours ( $\pm 2$  hours) after the start of Day 1 infusion
- Cycle 3 Days 4 ( $\pm 1$  day), 8 and 15 ( $\pm 2$  days)
- Cycle 3 Day 22: Pre-dose (only in patients with planned PK assessment)
- Cycle 4 and beyond: Pre-dose on Day 1

A single ECG will be obtained at the EOT visit.

## 7.6 Pharmacokinetic Assessments

Blood samples for PK assessments will be taken at approximately the following time points:

- Cycle 1 Day 1: Pre-dose (within 8 hours before treatment), within 15 minutes after EOI, and 2, 4, and 7 hours ( $\pm 15$  minutes) after EOI
- Cycle 1 Day 2: 24 hours ( $\pm 2$  hours) after the start of Day 1 infusion
- Cycle 1 Days 4, 8, and 15 ( $\pm 1$  day)
- Cycle 1 Day 22: Only applicable to patients whose scheduled Day 1 dose of the next cycle is delayed for  $\geq 3$  days or who cannot continue the next cycle of study treatment.
- Cycle 2 Day 1: Pre-dose (within 8 hours before treatment) and within 15 minutes after EOI
- Cycle 2 Days 8 and 15 ( $\pm 2$  days)
- Cycle 2 Day 22: Only applicable to patients whose scheduled Day 1 dose of the next cycle is delayed for  $\geq 3$  days or who cannot continue the next cycle of study treatment.
- Cycle 3 Day 1: Pre-dose (within 8 hours before treatment), within 15 minutes after EOI, and 2, 4, and 7 hours ( $\pm 15$  minutes) after EOI
- Cycle 3 Day 2: 24 hours ( $\pm 2$  hours) after the start of Day 1 infusion
- Cycle 3 Day 4 ( $\pm 1$  day), Days 8 and 15 ( $\pm 2$  days)
- Cycle 3 Day 22: Only applicable to patients whose scheduled Day 1 dose of the next cycle is delayed for  $\geq 3$  days or who cannot continue the next cycle of study treatment.
- Cycle 4 Day 1, Cycle 6 Day 1, and Cycle 8 Day 1: Pre-dose (within 8 hours before treatment)

Additional blood samples will be taken from patients who undergo IPDE.

- Day 1 of the first 4 cycles of IPDE: Pre-dose (within 8 hours before treatment) and within 15 minutes after EOI

*CONFIDENTIAL*

When ECG and PK assessments coincide, ECGs must be done **within** 10 minutes **before** the scheduled PK sample. When ECG and blood draws other than PK coincide, ECGs should be done before these blood draws, however these blood draws (other than PK) may be taken more than 10 minutes after ECGs, or ECGs may be done more than 10 minutes after these blood draws (other than PK). Additionally, a random PK sample may be drawn at any time during the study based on safety assessments of the patient.

At each PK time point, approximately 5 mL of blood will be collected. Instructions for the handling of blood samples and shipping of plasma samples for DS-6157a PK analyses are included in the Laboratory Manual. The actual time of DS-6157a administration (start of infusion and end of infusion) and the exact time of blood collection must be recorded on the eCRF.

The plasma PK parameters for DS-6157a, total anti-GPR20 antibody, and MAAA-1181a for each patient will be estimated using standard noncompartmental methods. The following PK parameters will be calculated: area under the plasma concentration-time curve up to the last quantifiable time ( $AUC_{last}$ ), area under the plasma concentration-time curve in the dosing interval ( $AUC_{tau}$ ),  $C_{max}$ ,  $T_{max}$ , and  $C_{trough}$  after the Cycle 1 and Cycle 3 doses. If data permit, the terminal elimination rate constant ( $K_{el}$ ), the  $t_{1/2}$ , elimination clearance (CL), the apparent volume of distribution at steady-state during terminal phase ( $V_z$ ), the apparent volume of distribution at steady-state ( $V_{ss}$ ), and area under the plasma concentration-time curve up to time infinity ( $AUC_{inf}$ ) will also be calculated.

Population PK and exploratory exposure-response analyses may be performed to further characterize the PK of DS-6157a, total anti-GPR20 antibody and MAAA-1181a, and the relationship between exposure and efficacy and/or safety endpoints. If performed, results of population PK or exposure-response analyses will be reported separately from the Clinical Study Report.

For the COVID-19 PK sampling schedule for chloroquine and hydroxychloroquine administration, see the [Assessment Schedule](#).

## 7.7 Anti-Drug Antibody Assessments

Blood samples (5 mL) for determination of potential anti-drug antibody against DS-6157a will be collected pre-dose from all patients treated with DS-6157a on Day 1 and Day 8 of Cycle 1, pre-dose on Day 1 of Cycle 2 to Cycle 4, and thereafter every 2 cycles from Cycle 4 through the EOT visit, and 30-day safety follow-up visit. Additional blood samples will be collected at pre-dose of the first 4 dosing cycles from patients who undergo IPDE. For patients with a positive ADA at the 30-day safety follow-up visit, an additional blood ADA sample should be collected every 3 months ( $\pm 1$  month) up to 1 year from the last dose of DS-6157a, or if the ADA becomes negative, or if ADA titer is equal to or less than baseline (applicable when pre-existing ADA is observed), or if the patient starts another therapy for cancer, or withdraws consent from the study, whichever occurs first.

Samples will be measured for the presence of ADAs using a validated bridging immunoassay. Tiered analysis will be performed to include screening, confirmatory, and titer assay steps and

*CONFIDENTIAL*

positive-negative cut points will be employed that were statistically determined from drug-naïve validation samples.

Immunogenicity will be assessed through characterization of incidence and titer of ADAs. The number and percentage of patients will be calculated for the presence or absence of ADAs before and after the start of study drug administration. Positive ADA samples will be stored for further assessments, and may include neutralizing antibody measurement when the assay becomes available.

Instructions regarding sample collection, sample handling/processing and sample shipping are provided in the Laboratory Manual in the Investigator Site File.

## **7.8 COVID-19 Antibody Testing**

If patient provides consent, samples should be collected prior to study drug infusion at Cycle 1 Day 1, Cycle 5 Day 1, every 4 cycles thereafter (Cycle 9, Cycle 13, etc.), and at the EOT visit. For patients with suspected or confirmed COVID-19 infections, follow the dose modifications in [Appendix H](#).

## **7.9 Biomarker Assessments**

### **7.9.1 Archival Tumor Samples**

Archival tumor samples, if available, will be collected at screening with the purpose of retrospectively identifying GPR20 expression status. Archival sample collection is recommended, but not mandated, and every effort should be made to obtain a sample. If the patient only has bone lesions that can be biopsied at the screening time, archival tumor sample taken from a non-bone lesion must be submitted. This material must be provided as a formalin-fixed paraffin embedded (FFPE) tissue block or 15 paraffin-dipped unstained slides. The status of GPR20 expression will be analyzed to explore whether these are correlated with the response to treatment.

### **7.9.2 Fresh Biopsies**

All patients will be required to undergo mandatory pre-treatment and on-treatment biopsies if the patient is clinically stable as judged by the Investigator. In addition, consenting patients may undergo an optional EOT tumor biopsy. If the patient agrees to the optional EOT biopsy, that biopsy must be obtained prior to the start of a new anticancer treatment. If IPDE is conducted, it is highly recommended to collect additional fresh biopsies after IPDE, if clinically feasible.

If the patient has multiple lesions suitable for biopsy, bone biopsy is to be avoided. However, if the patient only has bone lesions that can be biopsied, bone biopsy is still required for exploratory biomarkers assays.

Fresh biopsies will be used to retrospectively determine GPR20 expression status by protein and RNA level, if evaluable. Evaluable pre-treatment, on-treatment, and disease progression samples will be used for exploratory biomarker research such as topoisomerase relevant pathway markers and tumor microenvironment with protein and gene expression analyses. If possible, sites must collect pre- and on-treatment biopsies from the same tumor lesion. Failure to obtain sufficient

*CONFIDENTIAL*

tumor sample after making best efforts to biopsy the tumor will not be considered a protocol deviation. When feasible, collection of an optional tumor biopsy at EOT is encouraged, but will not be considered to be a protocol deviation if the patient declines the EOT biopsy. These samples will be used to investigate changes in pathway signaling and potential mechanisms of resistance (i.e., genetic alterations, or evidence of alternative pathway activation).

Fresh pre-treatment and on-treatment tumor biopsies are mandatory. All fresh biopsies will be processed according to the laboratory manual.

Core needle biopsies must be freshly taken after determination that the patient is eligible and before the first study drug treatment. If a pre-treatment biopsy during screening is not feasible or is unsafe, a pre-existing biopsy with equivalent quality collected after the termination of the most recent prior therapy and within 6 months of starting the first dose of DS-6157a will be acceptable. If a pre-existing biopsy collected within 6 months of starting DS-6157a is provided at screening (i.e., if the fresh pre-treatment tumor biopsy is not feasible or unsafe), the cfrNA and cfDNA samples will be collected at screening (within -28 to 0 days) and prior to DS-6157a infusion on Cycle 1 Day 1.

Another equivalent of four core needle biopsies must be collected at Cycle 2 between Day 8 and Day 15. Thereafter, collection of additional tumor biopsies is optional and can be performed between the EOT and follow-up visits prior to starting new treatments.

If IPDE is conducted, it is highly recommended to collect additional four core needle biopsies in the second cycle after IPDE, if clinically feasible. It should be collected between Day 8 and Day 15 of the cycle.

Sampling must be undertaken by experienced physicians in appropriate settings. The on-treatment biopsy can be omitted if clinically contraindicated or if the risk of the procedure for the individual patient has increased to a significant level.

Instructions regarding sample collection, sample handling/processing and sample shipping are provided in the Laboratory Manual in the Investigator Site File.

### **7.9.3 Blood Samples for cfDNA and cfrNA Analysis**

Two blood samples (2 × 10 mL) will be collected to provide plasma for cell-free (cf)DNA and one sample (1 × 10 mL) will be collected for cfrNA analysis to explore markers associated with response and/or resistance to DS-6157a and other exploratory biomarker research purpose. Each blood sample is to be collected at the following time points:

#### **cfDNA**

- Screening: within 7 days after the screening tumor biopsy but prior to the first infusion of DS-6157a on Cycle 1 Day 1
- Cycle 2 between Day 8 and 15, irrespective of biopsy date. However, collection on the same day as the tumor biopsy is recommended.
- Every 3 cycles thereafter (i.e., Cycle 5 Day 1, Cycle 8 Day 1, Cycle 11 Day 1 ...)
- EOT visit

*CONFIDENTIAL*

### **cfRNA**

- Screening: within 7 days after the screening tumor biopsy but prior to the first infusion of DS-6157a on Cycle 1 Day 1
- Cycle 2 between Day 8 and 15, irrespective of biopsy date. However, collection on the same day as the tumor biopsy is recommended.
- Cycle 5 Day 1: at the 12 week ( $\pm 7$  days) tumor assessment
- EOT visit

### **7.9.4 Exploratory Blood Biomarker Samples**

Blood sample for peripheral blood mononuclear cell (PBMC) and serum will be collected for exploratory analysis of biomarkers to assess the effect of DS-6157a on cytokines and chemokines, and on immune cells using methods such as flow cytometry and gene expression profiling. Biomarker blood samples will be taken at the following time points:

- Cycle 1 Day 1: Pre-dose
- Cycle 1 Day 8
- Cycle 2 Day 1: Pre-dose
- Cycle 3 Day 1: Pre-dose
- Any time that ILD is suspected

If IPDE is conducted, it's recommended to collect additional blood biomarker samples at the following time points:

- Pre-dose on Day 1 of first cycle of IPDE
- Day 8 of first cycle of IPDE
- Pre-dose on Day 1 of second cycle of IPDE

Pre-dose on Day 1 of third cycle of IPDE

Instructions regarding sample collection, sample handling/processing and sample shipping are provided in the Laboratory Manual.

### **7.9.5 Additional Biomarker Assessment**

In addition to the biomarkers specified above, exploratory biomarker research may be conducted on any samples. These studies would extend the search for other potential biomarkers relevant to the effects of DS-6157a, a malignancy and/or the resistance to the treatment. This may include the development of ways to detect, monitor, or treat malignancies. These additional investigations would be dependent upon clinical outcome, reagent and sample availability.

If the patient agrees, samples may be stored for a maximum of 15 years (or according to local regulations) following the last patient's last visit for the study at a facility selected by the sponsor to enable further analysis and address scientific questions of biomarker responses to DS-6157a and/or malignancies. Such analyses including genetic and genomic testing are exploratory in nature, and will not be performed using clinically approved diagnostic assays. Results from

*CONFIDENTIAL*

these exploratory assays have not been validated as appropriate for making treatment decisions for patients, and therefore the results will not be returned to patients or Investigators.

**7.9.6 Withdrawal of Consent for Use of Tissue Samples and Blood During the Study Period**

Patients have the right to withdraw permission for storage of biological samples for future research and the optional end-of-treatment biopsies, even if previously consented, and still continue on the study. Upon study withdrawal, if the patient exercises his/her right to withdraw permission for sample storage, any remaining specimens will be disposed of according to one of the procedures described below:

1. If specimens are temporarily stored at the study site, the Investigators will dispose of specimens from the withdrawing patient.
2. If specimens are stored at a specimen collection agency or analysis laboratories, the Investigators will report the site patient identifier or number to the Sponsor, and the Sponsor will direct the agency to dispose of the specimens.

If samples are already analyzed, Daiichi Sankyo is not obliged to destroy the results of this research.

**8. DRUG FORMULATION, AVAILABILITY, ADMINISTRATION, AND TOXICITY INFORMATION**

**8.1 DS-6157a**

Investigational Product	Dosage Form and Strength	Manufacturer
DS-6157a	100 mg lyophilized powder	Daiichi Sankyo

**8.1.1 Labeling, Packaging, and Supply**

DS-6157a will be supplied in an amber glass vial by Daiichi Sankyo as lyophilized powder.

Every 3 weeks, patients will receive DS-6157a intravenously by trained research staff. The research staff will document the amount of study drug administered. The batch number of the study drug dispensed to the patient must be entered on the eCRF, if applicable.

The immediate packaging will contain a statement to conform with FDA IND requirements as follows: “Caution: New Drug - Limited by federal (or US) law to investigational use.”

All study drugs must be kept in a secure place under appropriate storage conditions. Storage conditions for DS-6157a are included on the investigational product label.

The Sponsor or its representative must be granted access on reasonable request to check drug storage, dispensing procedures, and accountability records.

*CONFIDENTIAL*

### **8.1.2 Preparation and Administration of DS-6157a**

The first dose of DS-6157a in each patient will be infused for  $90 \pm 10$  minutes. If there is no infusion-related reaction after the initial dose, the subsequent dose of DS-6157a may be infused for  $30 \pm 5$  minutes based on the clinical judgment of the Investigator and/or Medical Monitor, but this reduced infusion rate is not mandatory.

Preparation and administration instructions will be provided in the pharmacy manual.

### **8.1.3 Precautions and Risks Associated with DS-6157a**

Precautions and risks are located in the IB.

## **8.2 Accountability for All Study Drugs**

The Principal Investigator (or designee) is responsible for accountability of all used and unused study drug supplies at the site.

All study drug inventories must be made available for inspection by the Sponsor or its representative (e.g., Innovations), and regulatory agency inspectors upon request.

Throughout the study and at its completion, Innovations Drug Accountability Record Form(s) or site inventory forms (if approved by Innovations) will be completed by the site and sent to the Innovations Regulatory Department. Study drug supplies must not be destroyed unless prior approval has been granted by the Sponsor or its representative. Please contact the Sponsor or its representative regarding disposal of any study drug.

## **9. RESPONSE EVALUATIONS AND MEASUREMENTS**

Response and progression will be evaluated in this study using RECIST Version 1.1 (see [Appendix B](#)). Lesions are either measurable or non-measurable according to the criteria. The term “evaluable” in reference to measurability will not be used, as it does not provide additional meaning or accuracy.

## **10. STATISTICAL CONSIDERATIONS**

### **10.1 Statistical Design**

This is a Phase I, two-part, multicenter, open-label, multiple dose first-in-human study of DS-6157a in patients with GIST. The primary objectives are to evaluate the safety, tolerability, MTD, RDE, and to investigate efficacy of DS-6157a.

### **10.2 General Statistical Considerations**

The data cut-off for the primary analysis will occur after all patients have either discontinued the study or have been followed for at least 6 months, whichever is earlier.

Data will be summarized by cohort and dose level, and overall when appropriate.

Descriptive statistics on continuous data will include mean, median, standard deviation, and range (as well as geometric mean and geometric coefficient of variation for PK data), while

*CONFIDENTIAL*

categorical data will be summarized using frequency counts and percentages. Graphical summaries of the data may be presented. Time to events endpoints will be reported using Kaplan-Meier estimates.

No statistical testing is planned for this study. If multiple doses or regimens are selected for Dose Expansion (Part 2), then no statistical comparison among the doses or regimens is planned.

Assessments of change from baseline to post-treatment or the ratio of post-treatment to baseline will include only those patients with both baseline and post-treatment measurements. The last non-missing value of a variable taken before the first dose of study drug will be used as the baseline value, unless otherwise specified. In general, missing data will not be imputed for the purpose of data analysis, unless otherwise specified.

A detailed statistical analysis plan (SAP) describing the methodology to be used in analysis will be prepared and finalized before database lock. Statistical methods described within this document may be changed based on advances in research.

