Treatment day (d)	Within -28 to 0 days	1	2	4 ±1 d	8 ±1 d	15 ±1 d	22 ±2d h	1 +2d	8 ±2d	15 ±2d	22 ±2d h	1 ±2d	2	4 ±2d	8 ±2d	15 ±2d	22 ±2d h	1±2d				
HIV, HBV, HCV testing a	X a																					
Eye exam f	X																			X		
Tumor assessment g	X a	Every 6 weeks (±7 days) in the first 36 weeks from Day 1 of Cycle 1, and every 9 weeks (±7 days) thereafter.																X g		X r		
Blood sampling for pharmacokinetics h		X	X	X	X	X	(X) h	X	X	X	(X) h	X	X	X	X	X	(X) h	X h				
Blood sampling for anti-drug antibodies (ADAs) i		X			X			X				X						X i	X i	X i	(X) i	
COVID-19 sample		X																	X s	X		
Blood sampling for cfDNA analysis j	X j								DAY 8 TO 15 j										X j	X j		
Blood sampling for cfRNA analysis k	X k								DAY 8 TO 15 k										X k	X k		

CONFIDENTIAL

Study Drug: DS-6157a

Sponsor/Innovations Study Numbers: DS6157-A-U101/GI 289

Final Protocol: 17 August 2021 Version 6.0

Study period	Screening	Dose Escalation and Dose Expansion DS-6157a Monotherapy Treatment Period																	EOT p	30-day Safety FU q	Long-term FU r		
		C1						C2				C3						C4+				After EOT	After 30-day Safety FU
Treatment day (d)	Within -28 to 0 days	1	2	4 ±1 d	8 ±1 d	15 ±1 d	22 ±2d h	1 +2d	8 ±2d	15 ±2d	22 ±2d h	1 ±2d	2	4 ±2d	8 ±2d	15 ±2d	22 ±2d h	1±2d					
Archival tumor sample (optional) l	X																						
Fresh tumor sample m	X							DAY 8 TO 15														(X) m optional	
PBMC and serum biomarker collection n		X			X			X				X											
DS-6157a infusion o		X						X				X							X				
Concomitant medication/procedures	X	X	X	X	X	X		X	X	X		X	X	X	X	X		X	X	X			
Adverse events p	X	X	X	X	X	X		X	X	X		X	X	X	X	X		X	X	X			
Patient status																					X	X	
PK Sampling for CQ/HCQ administration		If chloroquine (CQ) or hydroxychloroquine (HCQ) is administered for COVID-19, additional PK blood samples should be collected at the following visits, if feasible: 
 
• Prior to the first CQ or HCQ dose (Day 1)
 
																					

CONFIDENTIAL

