- Patient who meets any of exclusion criteria based on the most recent data, or who experienced ILD of any grade or any other dose modification toxicity event during DS-6157a treatment will not be eligible for IPDE.

IPDE may be conducted up to a dose that is 1 dose level below the dose already established to be safe and tolerable. Dose escalation should not be more than 3 dose levels at a time. The actual dose level will be decided based on the overall individual clinical status and PK profile. A patient may be allowed further IPDE after completing a minimum of another 4 cycles after the first IPDE, as long as the conditions for IPDE are met. AEs arising after IPDE should follow dose modifications/reductions per [Table 2](#), but further re-escalations will be prohibited after such events.

Dose can be delayed for up to 28 days from the planned date of administration. If a patient has a persisting AE/SAE that requires a longer dose delay, then patient will be withdrawn from the study after consulting with Medical Monitor.

Treatment cycles for a patient for whom DS-6157a dosing was temporarily withheld for any reason may have future cycles scheduled based on the date of the last DS-6157a dose. However, the tumor assessments will follow the pre-specified schedules relative to the start of the study treatment (Cycle 1 Day 1).

Investigators may contact the Medical Monitor or designee to discuss questions regarding dose modification or discontinuation of study drug.

All confirmed or suspected coronavirus disease 2019 (COVID-19) infection events must be recorded in the eCRF. Please refer to [Appendix H](#) for additional information on dose modifications.

*CONFIDENTIAL*

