### 10.5.2 Efficacy Analysis

Efficacy analyses will be based on FAS. If multiple doses or regimens were selected for Dose Expansion (Part 2) and not all randomized patients receive at least one dose of DS-6157a dose/regimen as randomized, sensitivity analyses will be performed for the Safety Analysis Set.

Efficacy variables will include BOR, ORR, DCR, CBR, DoR, TTR, and PFS using RECIST Version 1.1. In this study, best response determination using RECIST Version 1.1 requires confirmation of CR or PR.

A brief description of each endpoint is provided below.

- The BOR will be determined using tumor assessments performed before the start of any follow-up anticancer therapies (i.e. anticancer drug, radiotherapy, or surgery).
  - CR = at least two determinations of CR at least 4 weeks apart before progression.
  - PR = at least two determinations of PR or better at least 4 weeks apart before progression (and not qualifying for a CR).
  - SD = at least one SD assessment (or better) >6 weeks after randomization/starting treatment and before progression (and not qualifying for CR or PR).
  - PD = progression  $\leq$ 12 weeks from randomization/start of study treatment (and not qualifying for CR, PR, or SD).
  - NE = all other cases
- ORR is defined as the proportion of patients with BOR of CR or PR.
- DCR is defined as the proportion of patients with BOR of CR, PR, or SD.
- CBR is defined as the proportion of patients with BOR of CR or PR, or patients with SD lasting at least 180 days.
- DoR is defined as the duration from the first documented response to the date of progression or death due to any cause. In case a patient does not have progression or death, DoR is censored at the date of last adequate tumor assessment (defined as an assessment of CR, PR, or SD). DoR analysis will include only responders.
- TTR is defined as the time from randomization/start of study treatment to the date of first documented response. TTR analysis will include only responders.
- PFS is defined as the time from randomization/start of study treatment to the date of event defined as the first documented radiological progression or death due to any cause. If a patient has not had an event, PFS is censored at the date of last adequate tumor assessment.

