## **10.8 Analysis Time Points**

### **10.8.1 Primary Analysis**

The primary analysis of the study will occur after all patients have either discontinued the study or been followed for at least 6 months, whichever is earlier.

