### **10.8.2 Final Analysis**

The final analysis of the study will occur after all patients have discontinued the study. Data collected beyond the primary analysis cut-off will be presented as appropriate in a Clinical Study Report addendum.

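### The 6-month minimum follow-up for the primary analysis ends before the first scheduled scan that can document 180 days of stable disease, so CBR may be understated for the last patients enrolled

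*Combined protocol and SAP*

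**What the plan says.** - **Cut-off.** Section 10.2 sets the primary data cut-off after "all patients have either discontinued the study or have been followed for at least 6 months, whichever is earlier". Section 10.8.1 repeats this: "The primary analysis of the study will occur after all patients have either discontinued the study or been followed for at least 6 months".
- **Endpoint.** Section 10.5.2 defines CBR as the proportion with a confirmed response or "patients with SD lasting at least 180 days". Table 1 lists CBR among the Dose Expansion efficacy variables under the primary objective.
- **Scans.** The Assessment Schedule calls for tumor assessment "Every 6 weeks (±7 days) in the first 36 weeks from Day 1 of Cycle 1, and every 9 weeks (±7 days) thereafter". Section 7.3 uses the randomization date as the reference for randomized patients. Section 6 and the schedule footnotes keep scans on this calendar whether or not dosing is delayed.
- **Patients without an event.** Section 10.5.2 censors PFS and DoR at the last adequate tumor assessment. It gives no end date for SD duration and no rule for SD that is ongoing at the cut-off.
- **Denominator and missing data.** Efficacy uses all treated patients (Section 10.4), and missing data are generally not imputed (Section 10.2).
- **Later data.** Section 10.8.2: "Data collected beyond the primary analysis cut-off will be presented as appropriate in a Clinical Study Report addendum".

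**The concern.** The follow-up minimum and the SD threshold look matched, since 6 months is slightly longer than 180 days. SD is observed only at scans, however, and the scan calendar does not line up with either number. A patient can be alive, on treatment, progression-free and past day 180 at the cut-off, yet have no scan late enough to show it.

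If such patients stay in the denominator but not in the numerator, the primary-analysis CBR is too low for a reason tied to enrolment date rather than to the drug. The shortfall would fall on whichever cohort enrols last. That is probably Cohort 2, because the Figure 1 footnote opens it only after activity has been seen, but this is an inference. The same footnote uses SD of at least 6 months as part of the criterion for opening Cohort 2, so durable SD is a quantity the protocol itself relies on.

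**Working it through.** **The plan's own figure.** The plan gives no figure for this timing. The nearest is Table 3, which uses the interval method that Section 10.5.2 prescribes for CBR. Clopper-Pearson limits for 9 to 15 events in 30 reproduce all seven rows to 0.1 point (for example 11/30 = 36.7%, 90% CI 22.1-53.3).

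**Scan days.** Scan k falls on day 42k, ±7 days, to Week 36.

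| Scan | Nominal day | Window | Can show ≥180 days? |
|---|---|---|---|
| Week 18 | 126 | 119-133 | no |
| Week 24 | 168 | 161-175 | no |
| Week 30 | 210 | 203-217 | yes |

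The latest in-window Week-24 scan is 180 − 175 = 5 days short (4 days short if the first dose is counted as day 1). No routine on-treatment scan falls on days 176-202.

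**Cut-off against scans.** Six calendar months is 181-184 days. This assumes that follow-up is counted from the same reference date as the scans.
- To the opening of the Week-30 window: 203 − 184 = 19 to 203 − 181 = 22 days.
- To its close: 217 − 184 = 33 to 217 − 181 = 36 days.

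The earliest permitted cut-off therefore comes about 3 weeks before the Week-30 window opens and about 5 weeks before it closes.

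**Who is exposed.** With a last-scan end date for SD:
- A patient still on treatment with 182-202 days of follow-up has a last scheduled scan no later than day 175 and cannot reach 180.
- A patient with 203-217 days of follow-up is exposed only if the Week-30 scan has not yet been done.

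Taking 6 months as 182 days, the enrolment span before the last patient is 203 − 182 = 21 days at the least and 217 − 182 = 35 days at the most.

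**How many.** Accrual is not in the documents. Assume 30 patients accrue evenly:

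| Accrual period (assumed) | 21-day span | 35-day span |
|---|---|---|
| 6 months (182 days) | 30×21/182 = 3.5 | 30×35/182 = 5.8 |
| 12 months (365 days) | 30×21/365 = 1.7 | 30×35/365 = 2.9 |
| 24 months (730 days) | 30×21/730 = 0.9 | 30×35/730 = 1.4 |

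These are patients enrolled in the span. Only those in ongoing SD at the cut-off are miscounted.

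**Effect of each.** 1/30 = 3.3 points. As an illustration, if the true count is 12/30 (40.0%, 90% CI 25.0-56.6) and two patients are missed, the report shows 10/30 (33.3%, 19.3-49.9).

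**The case against.** **The miscount is not written in the plan.** A reader might infer that the protocol scores these patients as having no clinical benefit. It does not say so. If SD ran to the cut-off date, a patient with 181-184 days would qualify and the problem would vanish. This stands. The miscount is the natural reading, given the PFS and DoR convention, the all-treated denominator and the absence of imputation, but it is not an explicit rule. Sections 10.2 and 10.6 defer detail to a SAP, and the text supplied has no separate SAP section that closes the gap. Because the silence allows two opposite classifications of the same patient, it needs filling in any case.

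**Six months is a floor.** A reader might take the cut-off as fixed at 6 months. Section 10.8.1 says "been followed for at least 6 months, whichever is earlier" and requires the analysis to come after that point, so a cut-off at 31 weeks already complies. This stands: the problem arises only at or near the earliest permitted date. Nothing in the plan, however, steers the sponsor away from that date.

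**The size is easily inflated.** One might treat everyone with up to 217 days of follow-up as unscanned since day 175. From day 203 that is wrong, because the Week-30 scan may have been done. One might also quote a loss of about 10 points (5.8 × 0.5/30). That combines accrual of 30 patients in 6 months, Week-30 scans all done on the last allowed day, and half the patients in ongoing SD. The documents support none of these.

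**Some patients would progress at Week 30 anyway.** Whether they were miscounted depends on the missing rule. If only scans showing SD count, they never reach 180 days. If SD runs to the progression date, they do.

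**The stakes are limited.** No testing is planned, and the only efficacy conclusion rule (Section 10.3) rests on ORR. DCR does not use 180 days, and Kaplan-Meier PFS handles these patients by censoring. An unscheduled or end-of-treatment scan could rescue an individual. All of this stands and keeps the point modest.

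**Conclusion.** The timing mismatch is certain. It holds for any length of 6 months from 181 to 184 days, at either edge of the ±7-day window, and whether the first dose is day 0 or day 1. The downward bias in CBR is conditional on two things: a cut-off at or near the earliest permitted date, and SD measured to the last adequate scan.

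Under those conditions the exposed patients are those who started within roughly 3-5 weeks of the last patient. On the assumed accrual they number about 0.9 to 5.8 in a cohort of 30, of whom only those in ongoing SD are lost, at 3.3 points each. No single figure for the understatement can be given, because neither the accrual rate nor the proportion in ongoing SD is in the documents.

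A reader might also infer that the understated CBR is permanent or that it threatens the main efficacy conclusion. Neither follows. The final analysis can correct CBR, although its reporting is left to an addendum as judged appropriate, and the 36.7% ORR rule is unaffected. This is a worthwhile and cheap improvement to one efficacy endpoint listed under the Part 2 primary objective.

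**What to change.** 1. **Sections 10.2 and 10.8.1.** Set the primary cut-off to when every patient has discontinued the study or completed the Week-30 tumor-assessment window, that is, at least 31 weeks (217 days) from randomization or first dose.
2. **Section 10.5.2.** State that SD duration for CBR runs from randomization or first dose to progression or death or, if neither has occurred, to the last adequate tumor assessment. A patient in SD at Week 24 who is first found to have progressed at Week 30 then counts as having at least 180 days. The sponsor should adopt this knowingly and before the data are seen.

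Both changes are needed. The first ensures that the scan exists, and the second makes the classification reproducible.

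**Cost.** The earliest primary analysis moves by 33-36 days, about 5 weeks. No scans or patients are added.

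Keeping the 6-month cut-off and crediting SD from the Week-24 scan (day 161 onward) is not recommended. It would replace the 180-day endpoint with a different one, and it would sit badly with the 6-month SD criterion in the Figure 1 footnote.
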